12.2. Case Report Forms and Source Documents

The CRFs will be supplied by the CRO data management services. The complete CRFs will be reviewed, signed, and dated by the qualified investigator and a copy returned to the Sponsor with the final report.

Source documents are defined as original documents, data, and records. This may include hospital records, clinical and office charts, laboratory data/information, patients' diaries or evaluation checklists, pharmacy dispensing and other records, recorded data from automated instruments, microfiches, photographic negatives, microfilm or magnetic media and/or x rays.

12.3. Documentation and Retention of Essential Documents

All documents pertaining to the study, including a copy of the approved protocol, copy of the ICD, completed CRFs, source documents, drug accountability and retention records, and other study related documents will be retained in the permanent archives of the study site. These will be available for inspection at any time by the Sponsor or the FDA. Per 21 CFR 312, record retention for this study is required for a period of two years following the date on which this study agent is approved by the FDA for the marketing purposes that were the subject of this investigation; or, if no application is to be filed or if the application is not approved for such indication, until two years following the date on which the entire study is completed, terminated, or discontinued, and the FDA is notified.

The investigator will provide direct access to source data and documents for trial related monitoring, audits, IEC/IRB review, and regulatory requirements.

12.4. Financial Disclosure

These issues will be addressed in a separate agreement between the sponsor and the investigator.

The US FDA Financial Disclosure by Clinical Investigators (21 Code of Federal Regulations [CFR] 54) regulations require sponsors to obtain certain financial information from investigators participating in covered clinical studies; each investigator and sub-investigator is required to provide the required financial information and to promptly update Insys Development Company, Inc., with any relevant changes to their financial information throughout the course of the clinical

study and for up to one year after its completion. This rule applies to all investigators and sub-investigators participating in covered clinical studies to be submitted to the FDA in support of an application for market approval.

CONFIDENTIAL

13. FACILITIES

Selection of specific study vendors is pending.

14. **USE OF INFORMATION AND PUBLICATION POLICY**

14.1. Use of Information

All information concerning Cannabidiol Oral Solution and Insys Development Company's operations, such as Insys' patent applications, formulas, manufacturing processes, basic scientific data, or formulation information, supplied by Insys Development Company and not previously published, is considered confidential information.

This confidential information shall remain the sole property of Insys Development Company, shall not be disclosed to others without the written consent of Insys Development Company, and shall not be used except in the performance of this study.

The investigator will maintain a confidential patient identification code list of all patients enrolled in the study (by name and patient number). This list will be maintained at the site, and will not be retrieved by Insys.

Publication Policy 14.2.

Insys Development Company, Inc. will retain ownership of all data. All proposed publications based on this study will be subject to the sponsor's approval requirements.

2.1 Study Objectives

The objective of this study is to assess the long-term safety and tolerability of Cannabidiol Oral Solution (CBD) in patients with Prader-Willi Syndrome (PWS).

2.2 Overall Study Design

This is a multicenter, open-label study designed to assess long-term safety and tolerability of CBD in patients with PWS. Patients must have completed INS011-16-085 to be eligible for this study.

Patients may enroll in this long-term safety study after completing INS011-16-085 Visit 10 (Study Completion) to avoid interruption of the investigational medicinal product (IMP). Patients will have up to 2 weeks to enroll in INS011-17-115. If a patient does not enroll within the 2-week window, they will not be eligible to enroll into the study.

[figure not shown]
Patients will receive CBD treatment for approximately 48 weeks. Total daily doses ranging from 20 mg/kg/day to 40 mg/kg/day will be administered with standard meal. Patients may have their dose of study medication adjusted down once from 40 mg/kg/day to 30 mg/kg/day or from 30 mg/kg/day to 20 mg/kg/day at the discretion of the Investigator or qualified designee based on the patient's tolerability. If the lower dose is not tolerated, the drug will be discontinued and the patient will be withdrawn from the study.

The study consists of a Safety Period (48 \pm 2 weeks), Taper Period (6 \pm 3 days), and a Follow-up Period (30 \pm 5 days).

The study design is presented in Figure 1.

Sponsor Name: Insys Development Company, Inc.

Sponsor Protocol ID: INS011-17-115 Covance Study ID: 000000163385

All screening, efficacy and safety evaluations will be performed according to the schedule of assessments presented in Appendix A.

2.3 Sample Size and Power

The sample size is based on successful completion of INS011-16-085, with a maximum of 66 patients.

3. Efficacy and Safety Variables

3.1 Safety Endpoints

The safety endpoints for this study are:

- Incidence, type and severity of adverse events (AEs) and serious adverse events (SAEs) associated with CBD, i.e. treatment emergent adverse events (TEAEs)
- Changes from baseline in vital signs, physical exam, ECG findings and laboratory values (hematology, chemistry and urinalysis)
- Change from baseline in weight

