- Incidence, type, and severity of AEs and serious adverse events (SAEs) associated with Cannabidiol Oral Solution (i.e., treatment-emergent adverse events [TEAEs]).
- Changes from baseline in vital signs, ECG findings, and laboratory values (hematology, chemistry, and urinalysis).
- Change from baseline in weight.

Exploratory Efficacy Endpoint

• Change in total score of the HQ-CT from Baseline to Study Completion/Early Withdrawal.

Baseline is defined as Visit 10 of INS011-16-085.

Statistical Methods:

Safety Analysis

All safety assessments, including AEs, clinical laboratory evaluations, vital signs, 12-lead ECGs, and physical examination (including weight) will be listed for each visit. When appropriate, they will be summarized with descriptive statistics by age and dose cohort. The Medical Dictionary for Regulatory Activities (MedDRA; Version 20.0 or higher) will be used to classify all adverse events with respect to system organ class and preferred term. Adverse event summaries will include only TEAEs, which will be summarized for each treatment group.

- Clinical laboratory findings and vital signs will be summarized for all patients for observed values and change from baseline. Shifts from baseline to outside normal range criteria will also be presented for all patients.
- Weight will be listed and summarized for all patients for observed values and change from baseline. Shifts from baseline to outside normal range criteria will also be presented for all patients.
- Results of physical examinations conducted throughout the study will be presented in listings and summarized descriptively. Shifts from baseline according to normal and abnormal criteria will also be presented for all patients.
- Concomitant medications will be reported in the data listings.
- Statistical analyses will be performed using SAS® (Version 9.3 or higher, SAS Institute Inc.) or R (Version 3.3 or higher, Roswell Park Cancer Institute).

Missing Data

There will be no imputation of the missing values. All assessments will be conducted based on all the observed data.

Table 1: Schedule of Events

ASSESSMENTS SAFETY PERIOD			TAPER PERIOD	FOLLOW-UP PERIOD ^g			
Visit Number	1ª	2, 3, 4 (monthly)	5, 6 7 Early (quarterly) (End of Study) Withdrawal 8		Dai iy		9 (Phone Call)
Study Time Points	Day 1	Weeks 4, 8, 12	Weeks 24, 36	Week 48		0-6 Days	30 Days After EOS
Visit Window (Days)	± 5	± 5	± 5	± 3		± 3	± 5
Informed consent **	X			^			

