- There were no clear trends for age-related differences in cannabidiol exposures, but exposure in infants tended to be lower than that in children and adolescents, approximately half at the highest dose (40 mg/kg/day).
- Approximately 50% of subjects enrolled were receiving clobazam. Clobazam and cannabidiol have a reciprocal drug-drug interaction leading to the increased mean exposures of both cannabidiol (approximately 2.5-fold), and clobazam as well as norclobazam (approximately 3-fold) at the highest dose (40 mg/kg/day).
- No apparent gender differences were observed for cannabidiol pharmacokinetics (PK).
- Pharmacokinetic results for 7-hydroxy cannabidiol and its statistical evaluations generally reflected those observed for parent cannabidiol.
- There were no quantifiable levels Δ^9 -THC and 11-hydroxy- Δ^9 -THC measured following cannabidiol dosing.
- All doses of the investigational product were generally well-tolerated, although dose-titration was not employed. Dose-dependent adverse events (AEs) that occurred in multiple dosing cohorts and increased as the dose of the investigational product increased included diarrhea, flatulence, weight increase, somnolence, and psychomotor hyperactivity. Events of somnolence were potentially also related to concomitant use of clobazam with the investigational product, but this was not formally investigated in this study.
- There were no clinically relevant differences in the AE profile among subjects in the infant, child, and adolescent age categories.
- Serious adverse events were reported rarely and were consistent with underlying disease or procedures.

- Although this was not designed as an efficacy study, parent(s)/caregiver(s) and investigators both reported notable reductions in severity of mental illness (Clinical Global Impression of Severity) and improvement in global subject status (Clinical Global Impression of Improvement).
- The average change in weekly seizure rates (seizures of all types) was variable across subjects, dosing cohorts, and over time. Although the mean change in the weekly rate of tonic seizures at the end of the study compared with baseline generally decreased in a potentially dose-dependent manner, no pattern was observed for the other types of seizures reported. It was thought that tonic seizures were most representative of seizure control in this study.

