In addition, a long-term safety study (Protocol INS011-14-030) for subjects enrolled in the PK study above was recently completed. Fifty-two of 61 subjects from INS011-14-029 enrolled; 45 subjects completed the study. There were seven early termination subjects (two for withdrawal of consent, two for AEs of aggressions and sleepiness/irritability, one for the SAE of worsening seizures, one for lack of efficacy, and one subject with a genetic mutation died from systemic sepsis and multi-organ failure considered nonrelated). Overall, 91% of the subjects were taking doses greater than 20 mg/kg/day, with 38% of subjects tolerating 40 mg/kg/day. The most common drug-related AEs reported were anemia (5 subjects), somnolence (4 subjects), and weight increased (4 subjects). However, the weight increases ranged from a little over 2 lbs to approximately 7 lbs.

During the study, trough PK values were drawn and interim PK data for CBD and 7-OH CBD from Visit 5 (Week 4) to Visit 8 (Week 24) were analyzed. Dose-normalized mean trough CBD concentrations ranged from 11.9 to 16 (ng/mL)/(mg/kg), showing relatively stable levels for up to 6 months dosing Cannabidiol Oral Solution at various dose levels. After one month of dosing, there did not appear to be much accumulation, even though early accumulation had likely happened when compared with INS011-14-029 results. High variability in trough CBD concentrations was observed, but the extent of variability between visits was similar as reported in the previous 029 study.

An open-label study of Cannabidiol Oral Solution (20 mg/kg/day and 40 mg/kg/day) in pediatric subjects with infantile spasms refractory to ACTH and vigabatrin recently was halted due to futility (Protocol INS011-15-054) because only one out of nine patients achieved a complete response.

A food effect study of Cannabidiol Oral Solution in normal healthy adults (Protocol INS011-15-043) recently completed and the results are presented in the IB. Analysis demonstrated significantly higher CBD levels when administered with food.

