1.4. Prader-Willi Syndrome

Prader-Willi Syndrome (PWS), first described in 1956, is a multifaceted developmental disorder and the most common genetic syndrome associated with obesity (Gunay-Aygun et al., 1997; McAllister and Whittington, 2011). It is caused by the absent expression of paternally-inherited genes in the PWS region on 15q11-q13 (Ledbetter et al., 1981). While it presents with generalized hypotonia and developmental delay in infancy, PWS then manifests with uncontrollable appetite, hyperphagia, and excessive weight gain leading to severe obesity (Grechi et al., 2012).

Clinically, PWS patients suffer a complex pattern of physical, behavioral, endocrine, and intellectual deficiencies. Endocrine abnormalities lead to hypogonadism and short stature. In particular, growth hormone deficiency is reported to occur in 40% to 100% of the population (Griggs et al., 2015) and is commonly treated with growth hormone (Angulo et al., 2015). Behavioral disorders include obsessive compulsive behaviors such as skin picking, hoarding, redoing, and repetitive speech (Griggs et al., 2015).

However, it is the appetite behavior classified as hyperphagia in Prader-Willi Syndrome that is the most life threatening (Dykens et al., 2007; Griggs et al., 2015) and until recently, no patient lived over the age of 50 due to morbid obesity and its related complications (Aycan et al., 2014). The mortality rate in patients with PWS is six times higher than patients with other intellectual disabilities (Einfeld and Kavanagh, 2006) and mortality in patients not treated with growth hormone was estimated to be 3% per year between the ages of 6 and 56 compared to the general population mortality of 0.13% below 55 years. Mortality in Prader-Willi Syndrome below 5 years of age has not been determined (Eiholzer, 2005).

Hyperphagic behaviors can also be dangerous in persons who are not obese, with increased risks of death due to choking while sneaking food, and gastric perforations after consuming more food than usual (Dykens et al., 2007). Approximately 8% of deaths in individuals with PWS are reported due to the choking, especially on hot dogs (Stevenson et al., 2007). PWS patients also are known to eat discarded (contaminated) food and items that are not for human consumption such as pet food, or even non-food items such as paint or paper (Griggs et al., 2015).

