3. INVESTIGATIONAL PLAN

3.1. Overall Study Design

This is a multicenter, open-label study designed to assess long-term safety and tolerability of CBD in patients with Prader-Willi Syndrome. Patients must have completed INS011-16-085 to be eligible.

The investigator will ensure that the patients legal representative [parent(s)/caregiver(s)] will receive a copy of the informed consent form for review and provide full informed consent prior to study participation. Patients may enroll in this long-term safety study (INS011-17-115) after completing INS011-16-085 Visit 10 (Study Completion) to avoid interruption of the investigational product. Patients will have up to 2 weeks to enroll in INS011-17-115.

Patients will receive CBD treatment for approximately 48 weeks. Total daily doses ranging from 20 mg/kg/day to 40 mg/kg/day will be administered with standard meal. If any participant does not enroll within the 2 week window, that patient will not be eligible to enroll into the study.

The study will consist of a Safety Period (48±2 weeks), Taper Period (6±3 days), and a Follow-up Period (30±5 days). Treatment visits will be scheduled monthly for the first 3 months and then quarterly over the remaining 9 months. All patients will complete a Visit 7 (End of Study) or Early Withdrawal Visit regardless of when they stop treatment/complete the study. A Follow-Up telephone call (Visit 9) will occur 30 days after the end of either the End of Study (Visit 7) or Early Withdrawal.

Once the informed consent for INS011-17-115 is provided within the required time frame, the patient will receive a total daily dose ranging from 20mg/kg/day to 40mg/kg/day.

Patients will be dosed approximately every 12 hours with food to help ensure consistent plasma levels are achieved. Patients will be dosed for 48 weeks during which the investigator will assess safety and tolerability.

The study will be terminated upon one of the following:

- The investigational product is successfully approved for marketing in the US.
- Sponsor elects to terminate INS011-17-115.
- The patient has received 48 weeks of treatment.

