8.5.3. Safety and Tolerability Analyses

No formal inferential analyses will be conducted for safety variables. Data listings will be provided for protocol-specified safety data.

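### Weight and BMI are summarised without age and sex standardisation in an uncontrolled, apparently mainly paediatric 48-week study; the weight shift has no stated range and height is not in the visit schedule

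*SAP*

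**What the plan says.** **Endpoint and summary.** SAP 3.1 lists "Change from baseline in weight" as its own safety endpoint. The Protocol synopsis says "Weight will be listed and summarized for all patients for observed values and change from baseline", and promises shifts to values outside a normal range. SAP 6.7.4 places weight (kg), height (m) and BMI among the vital signs. All are summarised as observed values and change from baseline, by visit and treatment group, with a shift table to outside normal range. SAP 6.1 defines treatment group as the dose taken for longest, plus an all-CBD column, and sets baseline at Visit 10 of the parent study.

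**Age.** The synopsis says of the safety data: "When appropriate, they will be summarized with descriptive statistics by age and dose cohort". SAP 6.7.4 has no summary by age.

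**Inference.** Protocol 8.5.3: "No formal inferential analyses will be conducted for safety variables".

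**Weight on CBD.** For the sponsor's first paediatric study, Protocol 1.3 reports dose-dependent adverse events that "increased as the dose of the investigational product increased included diarrhea, flatulence, weight increase, somnolence, and psychomotor hyperactivity". For the 48-week extension it counts weight increase as drug-related in 4 subjects, adding: "However, the weight increases ranged from a little over 2 lbs to approximately 7 lbs". Protocol 1.6 closes by hoping for weight loss in this population.

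**Height.** Protocol 8.5.1.3 and 8.5.3.5 and SAP 6.4 and 6.7.4 all use it. Protocol Table 1, SAP Appendix A, footnote d to both, and the visit lists in Protocol Section 7 do not mention it.

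**The concern.** Children and adolescents are expected to gain weight over most of a year whether or not they take the drug. With no concurrent control, a mean change in kg cannot show how much is growth. Modal dose groups are not randomised, and Protocol 3.4 lets tolerability move patients between doses, so a different age mix could also look like a dose pattern.

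The direction matters here because the documents raise weight change both ways: gain as an adverse event, loss as the intended benefit. In a descriptive safety study the description is the result, so a named endpoint should be readable.

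Two documentary gaps add to this. The weight shift table needs a range that is not stated. BMI, the one planned measure that takes account of stature, needs a height that the schedule does not ask sites to record.

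**Working it through.** The plan states no figure to reproduce: the maximum of 66 patients (SAP 2.3) is a cap from the parent study, and neither document gives an expected growth, a standard deviation or a target difference for weight.

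**1. Is the population growing?** Protocol 1.3.1 gives 8-17 years. Protocol 3.1.1 applies the C-SSRS to ages 7 to 17. The eligibility criteria (3.2) set no age limit, and SAP 6.6.5 mentions adult C-SSRS forms. Mainly paediatric is a fair inference, not a stated fact.

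**2. How long is the span?** Baseline is Visit 10 of the parent study, enrolment may follow up to 2 weeks later, and the Safety Period is 48±2 weeks.
- Shortest: 48 − 2 + 0 = 46 weeks. Longest: 48 + 2 + 2 = 52 weeks.
- With the ±3-day Visit 7 window in Table 1 instead: (336 − 3)/7 = 47.6 to (336 + 3 + 14)/7 = 50.4 weeks.

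**3. What do the documents support as a drug effect?**
- 2 lb × 0.4536 = 0.91 kg; 7 lb × 0.4536 = 3.18 kg.
- Frequency: 4/52 = 7.7%, in patients with epilepsy.
- If only those four changed, the mean shift is 4/52 × 0.91 = 0.07 kg to 4/52 × 3.18 = 0.24 kg.

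No mean weight change across all 52 is given.

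**4. How large might growth be? (Assumptions, not from the documents and not specific to this syndrome.)** At constant BMI, gain = w0 × ((h1/h0)² − 1), with h1 = h0 + rate × 48/52.
- h0 = 150 cm, 2 cm/year, 40 kg: h1 = 151.8 cm, 2.5%, about 1.0 kg.
- h0 = 120 cm, 6 cm/year, 60 kg: h1 = 125.5 cm, 9.4%, about 5.7 kg.
- No height growth: 0 kg.

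A working range of 1 to 6 kg is therefore plausible for growing patients, but it remains assumed.

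**5. Comparison.** With growth of 1 to 6 kg, a neutral drug shows a mean of +1 to +6 kg. Adding 0.07 to 0.24 kg gives +1.07 to +6.24 kg. The two cannot be told apart, and growth exceeds the shift at least fourfold (1/0.24 = 4.2). A precise mean does not help: with 66 patients and an assumed SD of 3 to 8 kg, the 95% half-width is 1.96 × SD/√66 = 0.7 to 1.9 kg, around a mean that still contains growth.

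**6. Height, side by side.**

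| Relies on height | Omits height |
|---|---|
| Protocol 8.5.1.3 (baseline height and BMI) | Protocol Table 1 and SAP Appendix A, with footnote d |
| Protocol 8.5.3.5 (examination includes it) | Protocol synopsis visit lists and 3.1.1 |
| SAP 6.4 (cm, Day 1) | Protocol 6.1.1 and 6.1.2 |
| SAP 6.7.4 (m, by visit) | Protocol 7.1.1, 7.1.2 and 7.2 |

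SAP 6.4 says BMI is derived on the eCRF, so height is probably captured at Day 1. After Day 1 nothing schedules it. By-visit BMI may then be missing or rest on an old height, and the height behind baseline BMI (parent-study Visit 10 or Day 1) is not stated.

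**The case against.** **The analysis is descriptive.** This stands. No test or decision rule uses weight, so nothing inferential is at risk.

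**BMI is already planned.** A reader might infer that weight is examined in kg alone. SAP 6.7.4 contradicts that: BMI and its change are tabulated by visit. But raw BMI also changes with age, is not adjusted for sex, and depends on the unscheduled height.

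**The earlier weight gains.** A reader might take 0.9-3.2 kg as the expected mean effect and conclude that growth and drug effect are of equal size. The documents do not support this: those were individual events in 4 of 52 patients, in another disease.

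**Omission is weak evidence.** Protocol 6.1.1 also leaves out weight, which is plainly collected. So the inference that height is never measured is not supported; the gap is its scheduling after Day 1. Likewise, it is not shown that one kg range would be applied to all ages. The table shells are not among the documents supplied; what can be said is that no range is defined in those that are.

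**The data permit later standardisation.** Age, sex and weight are listed for each patient, and the synopsis allows summaries by age when appropriate. True, but an analysis chosen after seeing results carries less weight than one written down beforehand.

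**Standardisation does not isolate the drug.** This also stands. Protocol 1.4 says "growth hormone deficiency is reported to occur in 40% to 100% of the population", 4.7.1 allows growth hormone to be adjusted for weight, and change is measured from the end of the parent study. A neutral drug could still show a non-zero standardised change.

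**Conclusion.** The point holds as an interpretability problem. A named safety endpoint is reported on scales, kg and raw BMI, that are not standardised for age and sex, in an uncontrolled study of about 48 weeks in patients who appear to be mainly 8-17 years old. A mean kg change would mix expected growth with any drug-associated change.

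Its size cannot be fixed from the documents. The only illustration they allow is a mean shift of about 0.07 to 0.24 kg, assuming that nobody but the four reported patients changed. Growth of 1 to 6 kg would exceed it, but that range is an assumption, and in patients who have finished growing the issue largely disappears.

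The undefined weight range and the conflict over height are gaps in the text and need no assumption.

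Severity: a useful, inexpensive improvement. It is not an error affecting a planned inference.

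**What to change.** 1. **Standardised summary.** Keep change in kg as the endpoint. Add to SAP 6.7.4 a supplementary summary of change from baseline in age- and sex-standardised weight, and in standardised BMI where height was measured at that visit. Name the reference and use age at each visit. Add a summary by age band, as the synopsis allows. Report patients beyond the reference's age limit in kg and raw BMI only.
2. **Shift table.** Replace the undefined normal-range shift for weight with shifts between stated age- and sex-specific percentile categories.
3. **Height.** Reconcile the passages: either add height to Table 1, Appendix A, footnote d and Protocol Section 7 wherever BMI is tabulated, or limit the BMI tables to visits with a measured height. State which height is used for baseline BMI.
4. **Interpretation.** State that the weight results are descriptive, that change runs from the end of the parent study, and that standardisation removes reference-population growth only.

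**Cost.** Items 1, 2 and 4 need SAP wording, a reference lookup and a few more tables. Adding height to the schedule means a brief measurement at existing visits and a protocol change with written IRB approval (Protocol 10.4); limiting the BMI tables avoids that. The downside is more output and a general reference that may fit this population imperfectly.
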